Hysterectomy/ myomectomy	The surgery will be performed as per standard of care. A fibroid sample will be collected after the surgery.
Study duration	12 week treatment period, 18-20 weeks total.
Efficacy parameters	Tumor size: We will compare tumor volume pre and post-study using imaging techniques.
Feasibility parameters	
 • Subject retention: percentage of subjects who complete the study (as opposed to drop-outs). • Completeness of the outcome measures: percentage of subjects for whom treatment efficacy endpoints will be available by the end of the follow-up. • Adherence to the recommended treatment dosing: percentage of subjects who take at least 80% of the doses. • Clinical symptom improvement: We will use the validated uterine fibroid symptom and quality-of-life (UFS—QoL) (2) questionnaires to compare symptoms from pre and post-study assessment.
Safety parameters	
 • Percentage of adverse events (AE) and serious adverse events (SAE) by organ systems, including signs/symptoms, laboratory values, and clinical events. • Lab: We will compare hemoglobin, hematocrit, ferritin, liver enzymes and lipid panel pre and post-study.

A double blinded, phase II, randomized controlled trial to study the effects of simvastatin in patients with uterine leiomyoma.

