2.2 Feasibility Objectives

- 2.2.1 Clinical symptom improvement: We will use the validated uterine fibroid symptom and quality-of-life (UFS—QoL) (2) questionnaires to compare symptoms from pre and post-study assessment.
- 2.2.2 Subject retention: percentage of subjects who complete the study (as opposed to drop-outs).

- 2.2.3 Adherence to the recommended treatment dosing: percentage of subjects who take at least 80% of the doses.
- 2.2.4 Completeness of the outcome measures: percentage of subjects for whom treatment efficacy endpoints will be available by the end of the follow-up.

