All other anticipated or unanticipated adverse events not considered as serious adverse events will be reported to the FDA and IRB at the time of annual reports. The investigator will review accumulated adverse events after 30 subjects have completed the study, or earlier if the investigators notice any trend in complaints or abnormal laboratory results.

We plan to conduct first interim analysis after 30 subjects complete the study and if the results are sufficient to establish the primary hypothesis, safety and efficacy of the study drug, the study may be discontinued.

For all serious and/or unexpected adverse events, the PI will forward a copy of the adverse event report to the IRB and the FDA for the protocol.

Expected adverse events, (i.e., those events included as potential risks in the consent form) which are not serious, will be reported yearly on the Annual Progress Report (APR) for each protocol. A summary of all serious or unexpected side effects also will be included in the APR. If there were no adverse events, this will be stated in the APR. All serious adverse reactions occurring during the study, either observed by the physicians, nurses or reported by the subject, will be recorded on the Johns Hopkins Serious Adverse Event Case Report Form.

Potential risks are primarily those of simvastatin. We will counsel all study candidates about potential side effects of simvastatin as per prescribing information (1). The most important ones are muscle side effects such as muscle pain, tenderness, weakness or the more serious rhabdomyolysis. Other side effects include gastrointestinal (GI) side effects, liver function abnormalities, allergic reactions, headache, confusion, memory problems, fever, joint pain, cold symptoms, skin rash and sleep problems. The full list of side effects will be discussed at length with potential study candidates before signing of the consent form.

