8. CRITERIA FOR INTERVENTION DISCONTINUATION

Subjects will only receive the study drug simvastatin or placebo as a participant of the research study. Subjects may voluntarily withdraw from the study at any time and for any reason. The investigator may discontinue the subject's participation in the study if he believes it necessary for any reason including:

- 8.1 Intercurrent pregnancy
- 8.2 Symptom improvement where surgery is not necessary
- 8.3 Occurrence of an adverse event that precludes further participation in the study at the discretion of the investigator
- 8.4 Clinically significant adverse results in laboratory testing
- 8.5 Failure to comply with the protocol
- 8.6 Evidence of significant, persistent side effects

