10.2 Role of Data Management

Interval analysis may be conducted by a statistician. We expect that it may take 5 years to accrue 60 evaluable subjects for analysis and to complete the study procedures. The following types of data and processes will be the main focus for each subject:

- 10.2.1 Verification that informed consent was obtained appropriately prior to any study specific procedures and documented properly.
- 10.2.2 Adherence to protocol eligibility criteria.
- 10.2.3 Compliance with protocol procedures.
- 10.2.4 Documentation of procedures and assessments related to protocol-required safety assessments, evaluation and documentation of adverse events, especially any serious adverse events or withdrawals related to adverse events.
- 10.2.5 Conduct and documentation of study endpoints.
- 10.2.6 Procedures for documenting accountability and appropriate administration of the investigational product.

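### The only guaranteed review of accumulated adverse events waits for 30 completers, so withdrawals for toxicity push it later unless someone happens to notice a trend

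*Protocol*

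**What the plan says.** Section 7 fixes one investigator review of accumulated safety data: "The investigator will review accumulated adverse events after 30 subjects have completed the study, or earlier if the investigators notice any trend". The sentence goes on to name what may bring it forward: "or earlier if the investigators notice any trend in complaints or abnormal laboratory results". It gives no threshold or timetable for that early route. The next paragraph ties the interim analysis to the same count: "We plan to conduct first interim analysis after 30 subjects complete the study".

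Section 2.2.2 defines retention as "percentage of subjects who complete the study (as opposed to drop-outs", so a woman who drops out is not a completer. Section 8 allows the investigator to end participation for, among other reasons, "Occurrence of an adverse event that precludes further participation in the study" (8.3), clinically significant laboratory results (8.4) and "Evidence of significant, persistent side effects" (8.6).

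On timing, the synopsis gives "12 week treatment period, 18-20 weeks total" per woman, and section 10.2 states: "We expect that it may take 5 years to accrue 60 evaluable subjects for analysis". Section 3.2 anticipates 20% withdrawal and plans to recruit 72. Table 1 and section 6.4 place blood tests at screening and at Visit 4 (week 12) only. Section 3.3 blinds the study team, and section 10 gives the principal investigator sole responsibility for oversight.

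**The concern.** A safety review should be timed by how many women have been exposed, because exposure generates the risk. Here it is timed by how many women got through to the end. If the drug is poorly tolerated, women leave under section 8, the completer count grows more slowly, and more women start treatment before the one review that is certain to happen.

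The early route does not reliably repair this. It depends on a blinded team noticing a pattern with no stated criterion. One of its two named signals, abnormal laboratory results, is thin: the protocol schedules no on-treatment blood test before week 12, so a woman who leaves earlier adds no scheduled on-treatment result.

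**Working it through.** The figure of 30 completers is stated without a derivation (it is half of the target of 60), so there is nothing to reproduce. What can be checked is what the rule implies.

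**Inputs from the protocol**
- Trigger: 30 completers (section 7).
- Accrual: 60 evaluable women in 5 years, or 12 a year (section 10.2).
- Planned withdrawal: 20% (section 3.2).
- Time per woman: 12 weeks of treatment, 18–20 weeks in total (synopsis, section 3.4).

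**Assumptions**
- Accrual is uniform. Twelve evaluable a year at 20% withdrawal means 12 / 0.8 = 15 women starting treatment a year, both arms together. This rate is held fixed when withdrawal changes.
- Completion is not tied to a particular visit, so the lag L from first dose to completion runs from 12 weeks (12/52 = 0.231 years, end of treatment) to 19 weeks (19/52 = 0.365 years, middle of 18–20).
- The 40% withdrawal rate is illustrative, and 10% is added for contrast.

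**Formula.** With withdrawal proportion w, the 30th completion falls at the time t that solves (1 − w) × 15 × (t − L) = 30, so t = L + 2 / (1 − w). Women dosed by then = 15t.

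| w | 2/(1 − w), years | t, L = 12 wk | Dosed | t, L = 19 wk | Dosed |
|---|---|---|---|---|---|
| 10% | 2.22 | 2.45 | 37 | 2.59 | 39 |
| 20% (planned) | 2.50 | 2.73 | 41 | 2.87 | 43 |
| 40% (assumed) | 3.33 | 3.56 | 53 | 3.70 | 55 |

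**Delay.** From 20% to 40% withdrawal, the guaranteed review moves by 3.33 − 2.50 = 0.83 years, or 10 months. The lag cancels out of this difference.

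**Share of planned recruitment.** 41/72 = 57% to 43/72 = 60% at 20% withdrawal; 53/72 = 74% to 55/72 = 76% at 40%.

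**By arm.** Under 1:1 allocation about half of these women take simvastatin: about 21 at 20% withdrawal and about 27 at 40%.

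**Sensitivity to the accrual rate.** Using 72 / 5 = 14.4 a year with L = 19 weeks: at 20%, t = 30/(0.8 × 14.4) + 0.365 = 2.97 years and 14.4 × 2.97 = 43 dosed; at 40%, t = 30/(0.6 × 14.4) + 0.365 = 3.84 years and 55 dosed. The result barely changes.

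**If the excess is in one arm.** Suppose 20% withdraw on placebo and 60% on simvastatin (both assumed), which is 40% overall. Thirty completers then need 30 / 0.6 = 50 randomised women, 25 per arm. Of the 25 on simvastatin, 15 have left and 10 completed, so only 10 of the 30 women counted come from the arm with the problem.

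**Exposure-based comparison.** At 15 a year the 30th woman starts at 30 / 15 = 2.0 years. Six weeks later is 2.0 + 6/52 = 2.12 years, with 15 × 2.12 = about 32 dosed. Withdrawal does not enter the calculation.

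**The case against.** A reader might infer the stronger statement that the more women leave for toxicity, the later safety is reviewed. The documents do not support that. The same sentence in section 7 allows a review at any time once a trend is noticed, and toxicity that drives women out is just such a trend. Every woman is called weekly (sections 3.4 and 7), so complaints do not wait for completion. The pharmacist's assignment records are open to the study team at once in case of adverse events (section 3.3), so blinding is not absolute. Serious or unexpected events go individually to the IRB and FDA, other events go into annual reports (section 7), and section 5.1.1 promises a safety report on all participants. On the figures above, about two annual reports would come before the review. All of this stands.

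The size also deserves caution. The 20% is anticipated withdrawal from any cause, not toxicity. If placebo stays at 20%, an overall 40% needs 60% of the simvastatin arm to leave, and it is hard to imagine nobody noticing.

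A second tempting inference is that the review would look only at completers. Nothing says so: it covers accumulated adverse events, and only its timing depends on completers.

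What remains is that these safeguards are individual reports, reporting duties or discretion. The safety report in section 5.1.1 has no date. None of them is a scheduled cumulative look by the investigator, and none changes the trigger of the one that is scheduled.

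**Conclusion.** The point holds for the guaranteed review only. Its trigger counts completers, so withdrawal for toxicity delays it, and the sole way to bring it forward has no criterion and rests on a blinded team under one person's oversight. At the planned 20% withdrawal it falls when about 41 to 43 women have been dosed. At an assumed 40% it falls at about 53 to 55, roughly 10 months later, provided no trend is noticed meanwhile. These figures rest on uniform accrual of 15 a year, a 12- to 19-week lag and the assumed 40%; the direction does not. The other safety arrangements make this a change that should be made rather than a flaw that leaves women unmonitored. The point concerns when safety is reviewed, not the interim efficacy rule in the next paragraph of section 7.

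**What to change.** Replace the completer count in section 7 with an exposure trigger. The review takes place when 6 weeks have passed since the 30th woman's first dose, whether or not she or the women before her are still on treatment, or at a fixed calendar interval if that comes first. Keep the existing clause that allows an earlier review.

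The 6 weeks should be elapsed time, not attendance at Visit 3. Requiring the visit would again leave out women who stop in the first six weeks. It would also help to say that the review covers every woman dosed, with reasons for leaving, although this only makes explicit what the present wording implies.

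The cost is one or two sentences and no new data collection. The downside is less follow-up per woman at the first review and few scheduled on-treatment laboratory results, since none are taken before week 12. The review would also no longer coincide with the interim analysis, which keeps its own count.

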8. CRITERIA FOR INTERVENTION DISCONTINUATION

Subjects will only receive the study drug simvastatin or placebo as a participant of the research study. Subjects may voluntarily withdraw from the study at any time and for any reason. The investigator may discontinue the subject's participation in the study if he believes it necessary for any reason including:

- 8.1 Intercurrent pregnancy
- 8.2 Symptom improvement where surgery is not necessary
- 8.3 Occurrence of an adverse event that precludes further participation in the study at the discretion of the investigator
- 8.4 Clinically significant adverse results in laboratory testing
- 8.5 Failure to comply with the protocol
- 8.6 Evidence of significant, persistent side effects

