3.4 Study Duration

The participants will be enrolled in the study for a duration of 18-20 weeks. They will be visiting the study site 4 times for the study related visits and will be seen by the study team for follow up after their hysterectomy or myomectomy during their scheduled post-operative visits with their gynecologist. The first visit is the screening visit to obtain the informed consent and assess if the subject is eligible to participate in the study.

The study visits include:

1. Visit 1: Screening visit
2. Visit 2: Drug intake initiation visit at 0 weeks
3. Visit 3: 6 weeks after visit 2 during treatment period

4. Visit 4: 6 weeks after visit 3 during the treatment period

Follow up visits: Scheduled at subject's post-operative visits with their gynecologist for follow up.

The participant will receive the study medication at the treatment visits (Visit 2 and 3) for the next 6 weeks and study related assessments will be done at each of these visits. The study nurse will also remain in contact with the participant for the 12 week duration weekly to enhance compliance to study medication intake and to record adverse events if any.

The study nurse will also perform a drug reconciliation at each of the study visits to ensure that the patient is adherent to the study drug medication. The subjects will be instructed to bring all the medications that they forgot to intake or were left at the time of the research visit, these will be counted by the study nurse and a log of this information will be kept by the study research team. The regular weekly reminder calls from the study team will also complement the delivery of information about restricted food items such as grape fruit, cranberry juice for the intervals when the subject is not visiting the research team at Johns Hopkins Outpatient Clinic.

The subject undergoes hysterectomy or myomectomy at the end of treatment period (Visit 4) at week 12 and samples are obtained to study the fibroid tissue for molecular, cellular and histologic effects of simvastatin on human leiomyoma tissues. The study team will collect a 2.5 X 2.0 X 1.0 cm (or up to half of the tumor size) tissue sample from one fibroid for this study after the surgical pathology team has completed a preliminary evaluation of the delivered uterus. This tissue sample will undergo histopathological evaluation to study the effects of the study drug on fibroids.

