9. STATISTICAL CONSIDERATIONS

Exploratory data analysis will be used to evaluate variable distributions at study entry. Any unusual, outlying and out-of-range observations will be checked. Missing data patterns, especially due to drop-out, will be evaluated and reported. We will explore the distributions of potentially confounding variables, i.e. any demographic, family and medical history characteristics that are strongly predictive of the study efficacy outcomes. Differences in distributions of these potential confounders will be checked across the study arms as these might occur due to chance despite the randomization, especially for relatively small clinical trials (25). Results of these analyses will be used to refine the analyses and guide model building. The final model will include adjustments for the confounders that are differentially distributed by arm.

For feasibility endpoint, we will report the following proportions: subject retention, outcomes, and adherence to the study regimen, with their 95% exact binomial confidence intervals. Subject satisfaction score will be summarized (using mean and standard deviation) for the overall study sample and by treatment arm. Two-sided t-test will be used to compare subject satisfaction scores between the treatment arms.

Safety endpoint, including adverse events will be tabulated overall and by the study arm. Proportions of events by type across the treatment arms will be compared using Fisher's exact test. To account for multiple comparisons, false discovery rate (FDR) procedure will be used. FDR controls the expected proportion of incorrectly rejected null hypotheses ("false discoveries") at 5%.

Preliminary efficacy endpoint will be reported by treatment arm. Primary analysis will focus on 12-week outcomes. The efficacy outcomes will be compared across the treatment arms using generalized

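### Criterion 8.5 lets the investigator end study participation for non-compliance with no later follow-up, so a woman removed before Visit 4 has no 12-week tumour volume

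*Protocol*

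**What the plan says.** The title of Protocol section 8 concerns discontinuing the intervention. The sentence that governs the list goes further: "The investigator may discontinue the subject's participation in the study if he believes it necessary for any reason including". Item 8.5 is "Failure to comply with the protocol". It has no threshold, is not limited to missed doses, and is left to the investigator's judgement.

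The other provisions that matter are these:

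- **Primary outcome.** Section 6.3 names reduction in fibroid size, and section 9 places the primary analysis at 12 weeks. Table 1 (section 3.4) schedules ultrasound at Visit 1 and Visit 4 only.
- **After removal.** Neither Table 1 nor the visit descriptions in section 6.2 contain an early-termination visit or any follow-up of a woman whose participation has been ended.
- **Missing data.** Section 9 rules out imputing the primary outcome, limits multiple imputation to covariates, and promises sensitivity analyses for drop-out.
- **Feasibility.** Section 2.2 defines adherence as the "percentage of subjects who take at least 80% of the doses" and completeness as the "percentage of subjects for whom treatment efficacy endpoints will be available by the end of the follow-up". Retention sets completers against drop-outs. For these, section 9 says "we will report the following proportions: subject retention, outcomes, and adherence to the study regimen", with exact 95% intervals.
- **Monitoring of doses.** Section 3.4 has the nurse count leftover medication at study visits and telephone weekly.

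**The concern.** Stopping capsules and leaving the study are different events, and section 8 treats them as one. The trial watches capsule-taking closely, and 8.5 allows a woman to be taken out of the study for that behaviour. Once she is out, nothing brings her back for the ultrasound on which the primary comparison depends.

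The removal follows randomisation. Sections 3.6 and 7 list muscle and gastrointestinal side effects that could plausibly affect whether capsules are taken, so non-compliance need not be balanced between arms. If the arms lose different kinds or numbers of women, the 12-week difference is no longer a comparison of the groups as randomised.

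A second effect falls on the feasibility endpoints. An investigator's decision to remove a woman counts against retention, usually against completeness, and may settle her adherence result before her 12 weeks are over.

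**Working it through.** The plan states no figure for removals under 8.5, so there is none to reproduce. The check traces what happens to a removed woman's data and then bounds the size.

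**1. What data remain.** Take a woman removed at Visit 3.
- Tumour volume: screening value only. No ultrasound is scheduled at week 6 and she does not reach Visit 4.
- Primary 12-week model: she has no outcome, and outcome imputation is ruled out, so she drops out of the analysis.
- Mixed model over entry, week 6 and week 12: for tumour volume she supplies a baseline but nothing about change.
- Covariate imputation: not relevant to a missing outcome.

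**2. How many outcomes could be lost.** Inputs from section 3.2: 60 women, 30 per arm, 20% anticipated withdrawal, 72 recruited.
- Each removal: 1/60 = 1.7 percentage points.
- Six removals (assumed): 6/60 = 10%.
- Twelve removals: 12/60 = 20%, or 12/72 = 16.7% of those recruited. This assigns every anticipated withdrawal to 8.5, so it is an upper illustration and not a forecast.

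Recruiting 72 can restore the number analysed. It does not restore comparability, because the women lost are selected by their behaviour on treatment.

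**3. How removal can bias the comparison.** In one arm let p be the fraction removed, and let K, R and A be the mean outcomes of the women kept, the women removed, and the whole arm.
- A = (1 − p)K + pR, so K − A = p(K − R).
- Bias in the arm difference = p(K − R) in the simvastatin arm minus the same quantity in the placebo arm.
- Six removals, all in one arm of 30 (assumed): p = 6/30 = 0.20, so the bias is 20% of the gap between kept and removed women.
- Three removals per arm with the same gap in each: p = 3/30 = 0.10 in both, so 0.10 × gap − 0.10 × gap = 0.

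The bias thus depends on imbalance between arms in the removals or in the gap. The documents give no value for either.

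**4. Feasibility endpoints.** Daily dosing for 12 weeks is 12 × 7 = 84 doses; 80% is 67.2, so at least 68 are needed.
- A woman removed at Visit 3 has been supplied 6 × 7 = 42 doses. 42/84 = 50%, below 80%, so on the literal wording she counts as non-adherent.
- A woman who took 26 to 33 of the first 42 (62% to 79%) could still reach 68, since 26 + 42 = 68. Removal makes her a failure by decision.
- Retention falls 1/60 per removal, and so does completeness when Visit 4 is lost.
- Adherence rises only if removed women leave the denominator. With 48 of 60 adherent (assumed), the literal figure is 48/60 = 80.0% (exact 95% CI 67.7 to 89.2) however many of the 12 others are removed. Leaving out 4, 8 or 12 gives 48/56 = 85.7%, 48/52 = 92.3% or 48/48 = 100%.

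**The case against.** A reader might infer that 8.5 deletes non-adherent women and so inflates reported adherence. The documents do not support that. The endpoint is a percentage of subjects, not of completers, and no text takes discontinued women out of it. Dose counts up to the last visit are logged. On the literal reading a woman removed at Visit 3 is a counted failure, and early removal could even lower the adherence figure. Section 10.2 does speak of evaluable subjects without defining the term, but that alone does not establish an exclusion. The adherence denominator and a split of removals by who initiated them may be set in a statistical analysis plan that is not shown, so their absence here is not a fault.

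Further points on the other side are fair. The criterion is permissive and covers any protocol breach. The protocol's stated response to poor compliance is weekly contact. Items 8.3 and 8.6 already provide for exits due to adverse events and side effects, so only part of any tolerability effect would come through 8.5. Drop-out is to be reported and examined in sensitivity analyses.

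These points limit how often the problem may arise. They do not remove it. Sensitivity analyses show how far conclusions depend on missing ultrasounds, but they cannot supply them. An analysis plan cannot recover measurements that the protocol lets go uncollected.

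**Conclusion.** The point stands as one about follow-up and missing primary outcomes. Section 8 contradicts its own heading by ending study participation, and 8.5 allows this for a post-randomisation behaviour. With ultrasound only at screening and Visit 4 and no outcome imputation, each removal before Visit 4 loses that woman's primary outcome. Its size is 1.7 percentage points of 60 per removal. The bias in the treatment comparison is p(K − R) differenced between arms: nil if removals and gaps are balanced, and one fifth of the gap if six women are lost from a single arm of 30. The numbers of removals are assumptions, as is any link between non-compliance and tolerability. Retention, completeness and adherence are affected to the extent that 8.5 is used. Inflated adherence is not shown, because it requires an exclusion that the protocol does not state. The change should be made, since it prevents a loss that analysis can only describe.

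**What to change.** Reconcile the heading and text of section 8 by defining two separate events: stopping study drug, and leaving the study. State that non-compliance with dosing does not by itself end data collection. A woman to whom this applies, if she still consents, attends the scheduled Visit 4 for pill count, ultrasound and questionnaires, and is analysed in the arm to which she was randomised. Whether and when study drug is stopped remains with the investigator and is not touched by this change.

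The cost is an amendment to the wording and some effort to follow women who are not complying. Visit 4 is already in the schedule, so no new assessment is added. Including women who took little drug may dilute the estimated treatment effect; that is the price of keeping the randomised comparison.
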